3.1. Blinded Treatment Phase

Subjects who qualify for enrollment into the phase-2 portion of the study will be randomized in a 1:1 ratio to receive study treatment of EP with placebo or EP with tarextumab. The randomization will be balanced on the choice of platinum therapy (cisplatin versus carboplatin) and the prior use of whole brain radiation (WBR) or prophylactic cranial irradiation (PCI). Changing the choice of platinum therapy is not permitted once the subject is randomized. Treatment for each subject will begin on Cycle 1, Day 1 (the first dosing day). Etoposide 100 mg/m² will be given on Days 1, 2 and 3 and cisplatin 75 mg/m² or carboplatin to an AUC of 5 mg/mL/min will be given on Day 1 of every 21-day cycle for 6 cycles. Subjects may remain in the blinded treatment phase to continue one of the chemotherapy drugs if the other is held or discontinued prior to completing 6 cycles of EP and prior to disease progression. For subjects who have study drug held or discontinued for tolerability reasons, EP chemotherapy should continue to the completion of 6 cycles. Subjects may continue study drug if one or both of the chemotherapy drugs is held or discontinued prior to completing 6 cycles of EP and prior to disease progression.

After the completion of 6 cycles of EP, subjects who do not have disease progression and have not had WBR or PCI prior to study entry and are good candidates for PCI according to the

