8.1. Progression-Free Survival

On study tumor assessments are those that meet the following criteria:

1. No gap of >91 days between successive tumor assessments among those on or prior to the on study tumor assessment. (Note: a tumor assessment for which “Not Evaluated” is entered into the database does not qualify as a tumor assessment.)
2. No prior initiation of non-protocol anticancer therapy.

PFS, the primary endpoint of the study, is defined as the time from randomization (Day 1) until the first occurrence of death or disease progression based on investigator assessments of tumor response per the RECIST criteria. Progressions that are not determined from on study tumor assessments as well as deaths occurring more than 49 days from the last on-study tumor assessment are not treated as progression events. Subjects without a progression event will be censored at their last on study tumor assessment.

In addition two special cases will be handled in a manner consistent with the above rules as follows:

1. Patients whose first tumor assessment is >91 days from randomization will be censored on the date of randomization with a PFS of 1 day.
2. Patients who never had an on study tumor assessment and who did not die within 49 days (the scheduled time between tumor assessments plus 7 days) after randomization will be censored on the date of randomization with a PFS of 1 day.

The KM method will be used to estimate the proportions of subjects over time without progression or death and the median progression-free survival time. KM curves will be plotted by treatment group. The 95% confidence intervals for median progression-free survival time will also be calculated for each treatment arm. The p-value for treatment effect will be generated using a stratified log rank test using platinum choice (cisplatin or carboplatin; see page 6) and prior treatment modality (WBRT or PCI) as stratification factors. The HR and its 95% confidence interval will be estimated using a Cox proportional hazards (PH) model with main effects for treatment and the aforementioned stratification factors.

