According to the study design, administrations of randomized treatment (tarextumab or placebo only; without EP) may continue in 21-day cycles from the completion of 6 cycles of EP until the initiation of PCI. The following analysis of PFS will be conducted in order to determine if there is a treatment benefit when tarextumab is administered in combination with EP. Subjects who have not progressed will have their PFS censored 35 days (the scheduled time for 1 treatment cycle plus 7 days) following the last dose of Carboplatin/Cisplatin or EP. KM and Cox PH analyses will be the same as those described above.

The impact of the biomarkers Notch3, Hes1, Hey2, Hey1 and Hes6 on PFS will be evaluated with a Cox PH model with treatment, biomarker and treatment-by-biomarker interaction included in the model as independent variables. A separate Cox PH model will be used for each biomarker.

Sensitivity analyses for PFS include replicating the primary log-rank analysis using the PP population and unstratified log-rank tests using the ITT and PP populations.

The planned timing for the primary analysis of PFS is stated in section 5.5 above.

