8.2. Total Tumor Length

Total tumor length is the sum of the longest diameters (SLD) for the target lesions as defined by RECIST criteria. Standard summary statistics for a continuous variable (identified in section 5) will be computed for SLD at baseline and the Cycle-3, Day-1 (C3D1) and Cycle-5, Day-1 (C5D1) assessments. Summary statistics will also be presented for changes from baseline at the C3D1 and C5D1 tumor assessments. Ninety-five percent confidence intervals for the mean SLD at each time point will also be computed. Two analysis of covariance (ANCOVA) models for SLD will be used to test the hypothesis that there is no difference between treatment arms with regard to changes in tumor length from baseline at the C3D1 assessment.

- The difference between the follow-up and baseline SLD (e.g., $SLD_{C3D1} - SLD_{baseline}$) will be the dependent variable in the first ANCOVA model. Treatment, platinum choice (cisplatin versus carboplatin) and prior treatment modality (WBRT or PCI) will be categorical factors in the model, and $SLD_{baseline}$ will be included as a continuous covariate.
- The log of the ratio of follow-up to baseline SLD (e.g., $\log [SLD_{C3D1}/SLD_{baseline}]$) is the dependent variable in the ANCOVA model. Treatment, platinum choice and prior treatment modality will be categorical factors in the model, and $\log SLD_{baseline}$ will be included as a continuous covariate.

Missing values will not be imputed.

Separate but similar analyses will be performed for changes in tumor length from baseline at the C5D1 assessment.

A waterfall plot of best percent change in SLD across all tumor assessments relative to baseline will be presented.

Rates of change in SLD from baseline to C3D1, C5D1 and at progression will be evaluated.

The rate of change in SLD at CxD1 is defined as

$$100 \left(\frac{SLD_{CxD1} - SLD_{baseline}}{SLD_{baseline}} \right) / d_2$$

where d_2 is the number of days between the baseline assessment (Day 1) and the CxD1 assessment.

Rate of change in SLD at CxD1 will be missing for subjects who did not have a RECIST assessment corresponding to the CxD1 visit.

The rate of change in SLD from its on-study nadir to progression is defined as

$$100 \left(\frac{SLD_{progression} - SLD_{nadir}}{SLD_{nadir}} \right) / d_1$$

where d_1 is the number of days between the on-study SLD nadir and progression.

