Note: PFS= Date of Documentation of Death/Progression – Randomization Date + 1. Subjects who had not experienced death or progression by their last contact were censored at the time of their last radiographic response assessment. Subjects lacking a radiographic response assessment after randomization who do not progress or die have their event time censored on the date of randomization with duration of 1 day. For detailed event and censoring rules refer to protocol section 13.5.1 and SAP section 8.1. C.I. = Confidence Interval.

^[1] Sum of all individual follow-up times in days divided by 365.25.

^[2] The same censoring mechanisms used in the primary analysis of PFS were employed here. Additionally, for this analysis, a subject's PFS was censored 35 days (the scheduled time for 1 treatment cycle plus 7 days) following his or her last dose of etoposide or platinum.

^[3] Number of Subjects with Disease Progression or Death/ Total Follow-up Time (Person-years).

^[4] Hazard ratio and 95% C.I. from Cox proportional hazards model with main effects for treatment, platinum choice and prior treatment modality.

^[5] P-value for treatment effect from stratified log rank test using platinum choice and prior treatment modality as stratification factors.

Programmer notes: (a) repeat this table using the per-protocol population

Table 14.2.2.5
Progression-Free Survival – Impact of Biomarker Expression
ITT Population

Biomarker	Model Coefficients (SE) ^[1]		Hazard Ratio [95% Confidence Interval] ^[1]		
	Treatment x Biomarker Interaction		At 25 th Percentile	At 50 th Percentile	At 75 th Percentile
	Treatment	Interaction			
Notch3	xx.x (xx.x)	xx.x (xx.x)	xx.x [x.xx,xx.xx]	xx.x [x.xx,xx.xx]	xx.x [x.xx,xx.xx]
Hes1	xx.x (xx.x)	xx.x (xx.x)	xx.x [x.xx,xx.xx]	xx.x [x.xx,xx.xx]	xx.x [x.xx,xx.xx]
Hey2	xx.x (xx.x)	xx.x (xx.x)	xx.x [x.xx,xx.xx]	xx.x [x.xx,xx.xx]	xx.x [x.xx,xx.xx]
Hey1	xx.x (xx.x)	xx.x (xx.x)	xx.x [x.xx,xx.xx]	xx.x [x.xx,xx.xx]	xx.x [x.xx,xx.xx]
Hes6	xx.x (xx.x)	xx.x (xx.x)	xx.x [x.xx,xx.xx]	xx.x [x.xx,xx.xx]	xx.x [x.xx,xx.xx]

[1] Coefficients, hazard ratios and 95% confidence intervals are from Cox proportional hazards models with effects for treatment, biomarker and treatment-by-biomarker interaction. A separate model was used for each biomarker.

Programmer notes: (a) repeat this table using the per-protocol population

Table 14.2.2.7
Progression-Free Survival – Impact of Notch3 Expression in Subjects with High/Low Notch Pathway Markers
ITT Population

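### The 35-day cut in the combination-phase PFS analysis matches neither its stated derivation nor the 42-day scan interval, so after a last EP cycle of 1, 3 or 5 the next scheduled scan cannot count

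*SAP*

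**What the plan says.** SAP section 8.1 plans an extra PFS analysis to ask whether tarextumab helps while it is given together with EP. Subjects without progression "will have their PFS censored 35 days (the scheduled time for 1 treatment cycle plus 7 days) following the last dose" of platinum or EP. The shell for this analysis, Table 14.2.2.3, says in footnote [2] that "The same censoring mechanisms used in the primary analysis of PFS were employed here" and adds that a subject's "PFS was censored 35 days (the scheduled time for 1 treatment cycle plus 7 days) following his or her last dose", the dose being etoposide or platinum. The shell reports a hazard ratio, a confidence interval and a stratified log-rank p-value for ITT, repeated for the per-protocol population.

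The schedule comes from other sections. In section 3.1 platinum "will be given on Day 1 of every 21-day cycle for 6 cycles" and etoposide "will be given on Days 1, 2 and 3" of each cycle. Section 8.2 places tumor measurements at the "Cycle-3, Day-1 (C3D1) and Cycle-5, Day-1 (C5D1) assessments". Section 3.2 sets scans every 42 ± 5 days in follow-up. For deaths without a scan, section 8.1 uses a window built on the scan interval: "49 days (the scheduled time between tumor assessments plus 7 days".

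**The concern.** A window that closes PFS after the last dose should be long enough to include the scan that shows the disease status at the end of that treatment. This one is built on the treatment cycle, while progression is found at scans spaced two cycles apart. Whether the next scheduled scan can count then depends on whether the last EP cycle was odd or even, which has no scientific rationale.

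The cut is also set by stopping EP, which happens after randomization and can follow from toxicity or decline. If stopping differs between arms, the discarded scans may be informative in the one analysis meant to isolate benefit in combination with EP. Those scans should generally exist: a subject who stops EP without progression either continues study drug (section 3.1) or is scanned every 6 weeks (section 3.2).

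**Working it through.** **Derivation of the window.** The 49-day window reproduces: 42 + 7 = 49. The 35-day window does not: 21 + 7 = 28, and 35 would need a 28-day cycle.

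**Calendar.** For last EP cycle c, the last platinum dose is on day 21(c − 1) + 1 and the last etoposide dose 2 days later. Cut = last dose + 35. Scans: C3D1 = 21 × 2 + 1 = day 43; C5D1 = 21 × 4 + 1 = day 85; then 85 + 42 = day 127. Day 127 is an assumption that extends the 42-day spacing.

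| Last EP cycle | Last platinum / etoposide day | 35-day cut | Next scan | Scan inside? |
|---|---|---|---|---|
| 1 | 1 / 3 | 36 / 38 | 43 | No, 7 / 5 days late |
| 2 | 22 / 24 | 57 / 59 | 43 | Yes |
| 3 | 43 / 45 | 78 / 80 | 85 | No, 7 / 5 days late |
| 4 | 64 / 66 | 99 / 101 | 85 | Yes |
| 5 | 85 / 87 | 120 / 122 | 127 | No, 7 / 5 days late |
| 6 | 106 / 108 | 141 / 143 | 127 | Yes |

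**Visit window.** Applying the ± 5 days of section 3.2 to these scans (an assumption), the next scan after an odd cycle comes 42 ± 5 = 37-47 days after platinum, always outside 35. It comes 40 ± 5 = 35-45 days after Day-3 etoposide, inside only at the earliest edge.

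**Other lengths.**
- 28 days (the derivation taken literally): cuts on days 29/31, 71/73 and 113/115 after cycles 1, 3 and 5. It misses the same scans, even at −5 days.
- 42 days: reaches the nominal scan but not one at +5 days.
- 49 days: cuts on days 50/52, 92/94 and 134/136. It reaches the next scan after every cycle, including the latest case (47 days after platinum). After cycles 2, 4 and 6 its cuts (71/73, 113/115, 155/157) still precede the following scan (85, 127, and 127 + 42 = 169), so every stopper gets exactly one scheduled scan after the last dose.

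**Possible size, on assumptions only.** Simulations used the Table 3 control hazards, scans every 42 days and a true hazard ratio of 1. They assumed that 30% of subjects are frail (hazard × 2 to 3), that 5-10% of the others stop EP early, and that stops are spread evenly over cycles 1-5. A fixed cut at day 134 (127 + 7) served as reference.

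| Early stopping among frail subjects, tarextumab v placebo | HR with 35-day cut | HR with fixed day-134 cut |
|---|---|---|
| 60-70% v 20-25% | 0.94-0.97 | 1.00 |
| 40% v 20% | 0.98-0.99 | 1.00 |

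Across these scenarios the 35-day cut lost 9-14% of the events counted under the fixed cut. A 49-day cut lost 5-7% and gave hazard ratios of 0.97-0.99, so about half the bias remained.

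For scale, ln 0.94 = −0.06 and ln 0.98 = −0.02. With 91 events the standard error of the log hazard ratio is about 2/√91 = 0.21, so these shifts are about 0.3 and 0.1 standard errors. This analysis would have fewer events and a larger standard error.

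**The case against.** A reader might infer that anyone who stops EP after an odd cycle cannot have a PFS event. The documents do not support that. Death is an event and counts if it precedes the cut and meets the 49-day rule. A progression on an unscheduled scan before the cut counts. Listing 16.2.6.5 records non-radiographic clinical progression, although the SAP does not settle whether that is an event. An end-of-treatment scan in the protocol, which is not shown, could narrow the gap, and dose delays can move the next scan. What is lost is progression first seen at the next scheduled scan.

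Section 8.1 also literally censors only subjects without progression, so a later progression might still count; the loss described here needs the shell's wording. That reading is no defence. It would follow progressors beyond the cut while truncating everyone else, so censoring would depend on future outcome and the analysis would no longer be limited to the combination phase. The two texts need reconciling in any case.

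Progression found at C3D1 or C5D1 before that day's dosing makes the last cycle 2 or 4, inside the window, so many progression-driven stops are captured. This stands. The subjects affected are those who stop after an odd cycle for another reason.

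A reader might also infer that the rule favors tarextumab. That needs more early EP stopping on tarextumab, and the SAP gives no rates. Section 3.1 says EP should continue to six cycles when study drug is stopped for tolerability, which weakens the premise. Much of the simulated shift is ordinary informative censoring from any cut tied to the last dose, not the missed scan alone.

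**Conclusion.** The calendar defect stands on the SAP's own figures. The window is stated as 35 days, its derivation gives 28, and neither reaches the next scheduled scan after a last EP cycle of 1, 3 or 5. At 35 days the nominal shortfall is 5-7 days. Only the cycle-5 case depends on the extrapolated day 127.

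The consequence is limited. The lost events may be informative, but without stopping rates by cycle and arm neither the size nor the direction of bias can be known. The 0.94-0.99 range illustrates what assumed imbalances would do and is not an estimate for this trial. The analysis is supportive; the primary PFS test and the interim boundaries do not use this window.

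**What to change.** Change the sentence in section 8.1 and footnote [2] of Table 14.2.2.3 so that both state the same rule:

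- **Length:** 49 days, the SAP's scan interval plus 7 days, in place of 35 and its cycle-based explanation.
- **Anchor:** the last dose of platinum or etoposide, whichever is later. Section 3.1 lets one drug continue without the other, so the two last doses can be more than 2 days apart.
- **Scope:** events after the cut are not counted for any subject, whether or not progression follows.

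This costs one sentence and one footnote, needs no new data, and should be settled before unblinding. The window takes in up to 49 − 35 = 14 more days off EP, and some informative censoring remains.

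A fixed cut-off from randomization could be added as an optional sensitivity analysis. It removes the dependence on stopping EP, but it counts time off EP for early stoppers. Set at day 134, it would also close before the current cut for six-cycle completers (days 141-143) and make no allowance for dose delays.

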8.2. Total Tumor Length

Total tumor length is the sum of the longest diameters (SLD) for the target lesions as defined by RECIST criteria. Standard summary statistics for a continuous variable (identified in section 5) will be computed for SLD at baseline and the Cycle-3, Day-1 (C3D1) and Cycle-5, Day-1 (C5D1) assessments. Summary statistics will also be presented for changes from baseline at the C3D1 and C5D1 tumor assessments. Ninety-five percent confidence intervals for the mean SLD at each time point will also be computed. Two analysis of covariance (ANCOVA) models for SLD will be used to test the hypothesis that there is no difference between treatment arms with regard to changes in tumor length from baseline at the C3D1 assessment.

- The difference between the follow-up and baseline SLD (e.g., $SLD_{C3D1} - SLD_{baseline}$) will be the dependent variable in the first ANCOVA model. Treatment, platinum choice (cisplatin versus carboplatin) and prior treatment modality (WBRT or PCI) will be categorical factors in the model, and $SLD_{baseline}$ will be included as a continuous covariate.
- The log of the ratio of follow-up to baseline SLD (e.g., $\log [SLD_{C3D1}/SLD_{baseline}]$) is the dependent variable in the ANCOVA model. Treatment, platinum choice and prior treatment modality will be categorical factors in the model, and $\log SLD_{baseline}$ will be included as a continuous covariate.

Missing values will not be imputed.

Separate but similar analyses will be performed for changes in tumor length from baseline at the C5D1 assessment.

A waterfall plot of best percent change in SLD across all tumor assessments relative to baseline will be presented.

Rates of change in SLD from baseline to C3D1, C5D1 and at progression will be evaluated.

The rate of change in SLD at CxD1 is defined as

$$100 \left(\frac{SLD_{CxD1} - SLD_{baseline}}{SLD_{baseline}} \right) / d_2$$

where d_2 is the number of days between the baseline assessment (Day 1) and the CxD1 assessment.

Rate of change in SLD at CxD1 will be missing for subjects who did not have a RECIST assessment corresponding to the CxD1 visit.

The rate of change in SLD from its on-study nadir to progression is defined as

$$100 \left(\frac{SLD_{progression} - SLD_{nadir}}{SLD_{nadir}} \right) / d_1$$

where d_1 is the number of days between the on-study SLD nadir and progression.

Rate of change in SLD at progression will be missing for subjects who did not have a RECIST assessment of PD on study and for subjects whose on-study $SLD_{nadir} = 0$.

Comparisons of these rates of change between the two treatment arms will be made using an analysis of variance (ANOVA) model with treatment, platinum choice (cisplatin versus carboplatin) and prior treatment modality (WBRT or PCI) as categorical independent variables.

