5.3. Missing Values

No imputations will be made for missing values. Summaries will be based on observed data only.

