Note: tumor length is calculated as the sum of the longest diameters (SLD) for the target lesions. SD = Standard Deviation; LS = Least Squares; SE = Standard Error; C.I. = Confidence Interval.

^[1] The difference between the follow-up and baseline SLD (e.g., $SLD_{C3D1} - SLD_{baseline}$) is the dependent variable in the ANCOVA model for change from baseline. Treatment, platinum choice (cisplatin versus carboplatin) and prior treatment modality (W/BRT or PCI) will be categorical factors in the model, and $SLD_{baseline}$ will be included as a continuous covariate.

^[2] The log of the ratio of follow-up to baseline SLD (e.g., $\log [SLD_{C3D1}/SLD_{baseline}]$) is the dependent variable in the ANCOVA model for percent change. Treatment, platinum choice and prior treatment modality will be categorical factors in the model, and $\log [SLD_{baseline}]$ will be included as a continuous covariate.

Programmer notes: (a) repeat this table using the per-protocol population

Table 14.2.4.3
Rate of Change in Total Tumor Length at Progression
ITT Population

	Placebo (N=xx)	Tarextumab (N=xx)
SLD at Nadir		
n	xx	xx
Mean (SD)	xx.x (xx.xx)	xx.x (xx.xx)
Median	xx	xx
25 th , 75 th Percentile	xx, xx	xx, xx
Min, Max	xx, xx	xx, xx
SLD at Progression		
n	xx	xx
Mean (SD)	xx.x (xx.xx)	xx.x (xx.xx)
Median	xx	xx
25 th , 75 th Percentile	xx, xx	xx, xx
Min, Max	xx, xx	xx, xx
Rate of SLD Change from Nadir to Progression (%/day) ^[1]		
N	xx	xx
Mean (SD)	xx.x (xx.xx)	xx.x (xx.xx)
Median	xx	xx
25 th , 75 th Percentile	xx, xx	xx, xx
Min, Max	xx, xx	xx, xx
P-value ^[2]		0.xxx

Note: SLD = Sum of Longest Diameters (i.e., total tumor length for target lesions as defined by RECIST criteria [version 1.1]).

^[1] Rate of Change in SLD at progression = 100 x (SLD at Progression – SLD at Nadir) / SLD at Nadir / (number of days between nadir and progression).

^[2] P-value for treatment effect from ANOVA model with treatment, platinum choice and prior treatment modality as categorical independent variables.

Programmer notes: (a) repeat this table using the per-protocol population

Table 14.2.4.5
Rate of Change from Total Tumor Length at Baseline
ITT Population

	Placebo (N=xx)	Tarextumab (N=xx)
SLD at Baseline		
n	xx	xx
Mean (SD)	xx.x (xx.xx)	xx.x (xx.xx)
Median	xx	xx
25 th , 75 th Percentile	xx, xx	xx, xx
Min, Max	xx, xx	xx, xx
SLD at Cycle 3, Day 1		
n	xx	xx
Mean (SD)	xx.x (xx.xx)	xx.x (xx.xx)
Median	xx	xx
25 th , 75 th Percentile	xx, xx	xx, xx
Min, Max	xx, xx	xx, xx

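### The log-ratio ANCOVA of tumor length has no value when target-lesion SLD is 0, so that one supportive model drops patients because of their outcome

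*SAP*

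**What the plan says.** Section 8.2 defines the measure: "Total tumor length is the sum of the longest diameters (SLD) for the target lesions as defined by RECIST criteria". Two ANCOVA models test for no difference between arms at C3D1, and similar models are planned at C5D1.

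- The first has as its dependent variable "The difference between the follow-up and baseline SLD", with baseline SLD as covariate.
- The second uses "The log of the ratio of follow-up to baseline SLD", with log baseline SLD as covariate.

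Both carry treatment, platinum choice and prior treatment modality as factors. The section adds "Missing values will not be imputed", and section 5.3 says in general "No imputations will be made for missing values".

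The section foresees an SLD of zero in one place. The rate of change from nadir to progression is set to missing "for subjects whose on-study $SLD_{nadir} = 0". Neither ANCOVA has such a rule.

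In Appendix B, footnote 2 to Table 14.2.4.1 says that the log ratio "is the dependent variable in the ANCOVA model for percent change". The table prints that p-value in the Percent Change column, under the mean, median and range of percent change.

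**The concern.** If all measured target lesions are gone, follow-up SLD is 0 and the logarithm of 0 over baseline has no value. The SAP does not say that such patients are excluded. It follows from three facts taken together: the response is undefined, no rule replaces it, and nothing is imputed.

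The exclusion is decided by the outcome under test, and the patients removed are those with the largest possible shrinkage of target lesions. If the arms differ in how often this happens, randomization no longer protects the comparison among those who remain. Percent change, by contrast, is well defined for these patients (-100%). The p-value and the summaries above it would therefore describe different sets of patients, and the table shell has no line that says so.

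**Working it through.** The SAP states no power or effect size for tumor length and no frequency of SLD = 0, so there is no figure to reproduce. The algebra comes from the document; every rate below is an assumption.

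**1. Which analyses are defined at SLD = 0** (baseline SLD = B)

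- Difference ANCOVA: 0 - B = -B. Defined.
- Log-ratio ANCOVA: log(0/B). Undefined.
- Percent change (Table 14.2.4.1 summaries, waterfall plot): 100 × (0 - B)/B = -100. Defined.
- Rate from baseline to CxD1 (Table 14.2.4.5): -100 divided by days. Defined, and missing only when the visit has no RECIST assessment.

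Only the log-ratio model loses the patient.

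**2. How many are lost** (assumed 58 assessed per arm, 116 in all)

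- Zeros 3% vs 15%: 58 × (0.03 + 0.15) = 10.4
- Zeros 5% vs 20%: 58 × (0.05 + 0.20) = 14.5
- Zeros 2% vs 5%: 58 × (0.02 + 0.05) = 4.1

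**3. Disappearance unrelated to other shrinkage.** Assume the log ratio among non-zero patients is normal with mean -0.6 and SD 0.4 in both arms. The patients left in the log-ratio model then have the same distribution in each arm, so its expected effect is 0 whatever the zero rates. On the percent-change scale the mean ratio of non-zero patients is exp(-0.6 + 0.4²/2) = 0.595. At 3% vs 15% the effect is (0.15 - 0.03) × (-59.5) = -7.1 points.

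Simulated rejection rates (two-sided 5%, 58 per arm, baseline log SD 0.5, visit day 42 ± 5):

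| Test | 3% vs 15% | 5% vs 20% |
|---|---|---|
| Log-ratio ANCOVA (planned) | 5% | 5% |
| Difference ANCOVA (planned) | 21.1% | 28.1% |
| Rate-of-change ANOVA (planned) | 25.9% | 34.4% |
| Percent-change ANCOVA | 25.8% | 34.1% |
| Rank ANCOVA | 19.9% | 27.4% |

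The log-ratio test stays at its nominal level: it has no power for this kind of benefit. At 2% vs 5% every method rejects in 5% to 7% of trials, so little separates them.

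**4. The strongest shrinkers are the ones who disappear.** Now the zeros replace the lowest fraction p of log ratios. The mean of those who remain rises by SD × φ(z_p)/(1 - p), where z_p is the normal quantile at p and φ the normal density.

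- SD 0.4, p = 0.03: rise 0.028. p = 0.15: rise 0.110. Difference +0.082, in favour of placebo.
- SD 0.5, p = 0.02: rise 0.025. p = 0.20: rise 0.175. Difference +0.150.

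Simulation agrees. At 3% vs 15% (58 per arm) the mean effect is +0.08, and placebo is significantly favoured in about a quarter of trials (24% and 26% in two runs). With 67 per arm, SD 0.5 and 2% zeros on placebo:

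| Zeros on tarextumab | Mean log-ratio effect | Significant for placebo | Significant for tarextumab |
|---|---|---|---|
| 2% | -0.003 | 2.9% | 4.3% |
| 5% | +0.027 | 6.7% | 2.1% |
| 10% | +0.072 | 17.8% | 1.1% |
| 20% | +0.150 | 45.1% | 0.1% |

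The models that keep zeros do not reverse. At 2% vs 20% the difference ANCOVA favours placebo in 0.3% of trials and the rank ANCOVA in 0.7%. At 3% vs 15% and 5% vs 20% the percent-change ANCOVA does so in at most 0.2%. They gain little power here, however: percent-change and rank models favour tarextumab in only about 3% to 10% of trials.

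**5. Why a floor value is not a neutral repair.** With baseline 100 mm and a floor of 5 mm, a zero becomes log(0.05) = -3.0. With mean -0.6 and SD 0.5, that is (-3.0 + 0.6)/0.5 = -4.8 SDs from the mean. At 2% vs 20%, 0.18 × (-3.0 + 0.6) = -0.43 (simulated -0.432), so the whole estimated effect depends on the floor chosen.

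**The case against.** The strongest reply is that the plan already holds what is needed. The difference ANCOVA tests the same hypothesis and keeps zeros. The rate-of-change ANOVA is percent change divided by days, with the same factors, and rejects as often as a percent-change ANCOVA (25.9% against 25.8%). The waterfall plot and ORR also keep these patients. Tumor length is in none of the stated objectives, and with few zeros the effect is small. Footnote 2 does disclose that the p-value comes from a log-ratio model.

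All of this stands, and it limits the point. A reader might infer that the tumor-length analysis as a whole cannot see disappearance; it can, through these other analyses. A reader might also infer that the bias always runs toward no difference. That holds only when disappearance is unrelated to other shrinkage; otherwise the sign can reverse. Nor is SLD = 0 the same as complete response. Listing 16.2.6.2 records the short axis for lymph nodes, so a resolved node can leave SLD above 0, and SLD can be 0 without an overall CR.

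The reply does not remove the defect. One of two formally stated tests has a dependent variable with no value for an outcome the section itself foresees. Footnote 2 names the model but does not reveal that its patients differ from those summarized above it.

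**Conclusion.** The point holds for one supportive model. As written, the log-ratio ANCOVA at C3D1 and C5D1 excludes patients with target-lesion SLD of 0 at that visit because of their outcome. It is then blind to a benefit expressed as disappearance and can favour placebo if the best shrinkers disappear. Its p-value in Table 14.2.4.1 rests on fewer patients than the percent-change summaries beside it.

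The size depends on the rate of SLD = 0, which the document does not give. Under the assumed 3% vs 15%, about 10 of 116 patients are lost and the test either has no power or favours placebo in about a quarter of trials. At 2% vs 5% about 4 are lost and the effect is small. PFS and OS are not touched, and the other tumor-length and response analyses keep these patients. The change should be made because it is cheap and removes a misleading p-value; no main conclusion hangs on it.

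**What to change.** Before unblinding, replace the second model by an ANCOVA on percent change from baseline, with SLD = 0 entered as -100%. Keep treatment, platinum choice and prior treatment modality as factors and use baseline SLD as covariate. The p-value and the summaries in the Percent Change column then use the same patients. The gain is that consistency and the end of outcome-driven exclusion; it adds no power over the planned rate-of-change ANOVA.

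If the log-ratio model is kept, label it supportive and print the number of SLD = 0 patients excluded, by arm and visit, in Table 14.2.4.1. A rank ANCOVA with zeros ranked best is an acceptable sensitivity analysis, but it gains little when the best shrinkers disappear.

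The cost is a change of SAP wording, one table footnote and one model call. The downside is that the effect is no longer a ratio and that percent change is more skewed than its logarithm.
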